To our knowledge, none of the faculty in the pediatric otolaryngology department at CHC has conducted any research studies the effectiveness of different treatments of tracheostomy granulomas.

IV. Research Methods

A. Outcome Measure(s):

1. Success or failure of treatment method
 - a. Definition of success: We are defining successful treatment of tracheostomy granulomas as a clinically significant decrease in the size of granuloma (greater than 50% improvement) over a six week observation period using the assigned treatment.
 - b. Definition of failure: We are defining a treatment as a failure as if there is less than 50% reduction in size of tracheostomy granulomas at the conclusion of the six week observation period or if worsening occurs requiring alternative treatments.
2. Categorical Improvement (Degree of Improvement)
 - a. At each time point, the size of the granuloma will be measured and recorded. The percent circumference will also be measured
 - b. The approximate percent decrease in the granuloma size will be determined to determine the category subject's change in granuloma:
 - i. Complete resolution: >90% improvement (Score = 4)
 - ii. Improvement: 50 - 90% improvement (Score = 3)
 - iii. Minimal improvement: < 50% improvement (Score = 2)
 - iv. No improvement (Score = 1)
 - v. Worsening (Score = 0)

B. Description of Population to be Enrolled:

The population to be enrolled in this study includes all Children's Hospital Colorado patients, 31 days to 18 years of age inclusive, who are being treated for a tracheostomy granuloma and consent to participating in the study. We anticipate 45 patients will be needed for this pilot study to determine the effect size and variation in granuloma change.

C. Study Design and Research Methods:

The study will be a prospective comparison of three different treatment methods for patients with tracheostomy granulomas at Children's Hospital Colorado. The current standards of care for tracheostomy granulomas that we will be examining include: steroid application, silver nitrate and betadine. Patients or parents will be consented or assented during the initial physician visit prior to any administration of treatment by the provider. The treatment method will be assigned starting at the time the patient is enrolled in the study.

1. The three treatment methods (steroid application, silver nitrate, and betadine) will be assigned sequentially #1, #2, or #3. (See below for description)

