2. Patients will be assigned a treatment method based on the sequential allocation done prior to enrollment. To reduce potential bias, the enrolling physicians will be unaware of the previous patient's allocated treatment group.
3. The treatment method for the patient given at the initial visit will be documented in Epic. During the six week observation period, the study team will collect follow-up data on the degree of improvement for each treatment method. Our primary time point will be 6 week follow up.
4. Each patient will be followed for an observation period of six weeks, with follow-up appointments, per standard of care, every two weeks (+/- 3 days) in order for a physician to evaluate the degree of improvement for each treatment method. If the investigator determines further follow-up is not necessary, per standard of care, the observation period will end.
5. If during a follow-up visit, the physician determines the patient's granuloma is worsening, the follow-up period will end and the patient's participation in the study will be complete. If

other treatments are utilized, we will analyze with the intent to treat analysis based on the treatment the subject was received.

[figure not shown]
6. In addition, if a patient is given a different form of treatment, such as in the emergency department or through a primary care physician, the follow-up period will end and the patient's participation in the study will be complete.

Treatments:

- 1) Silver nitrate – Silver nitrate will be applied to the tracheostomy site granuloma after enrollment. Parents will be instructed to keep the site dry for 14 hours. Residual granuloma will be treated similarly at Follow up #1 and #2, but not at Follow up #3.
- 2) Betadine solution will be used to topically treat the tracheostomy site BID for 2 weeks (until Follow up #1). If residual granuloma is present, an additional week will be recommended and this treatment duration recorded.
- 3) Hydrocortisone 1% topical will be used to topically treat the tracheostomy site BID for 2 weeks (until Follow up #1). If residual granuloma is present, an additional week will be recommended and this treatment duration recorded.

Study Design Flow Chart

Sequential allocation of treatment methods (steroid application, silver nitrate, or betadine)

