Definition of success: We are defining successful treatment of tracheostomy granulomas as a clinically significant decrease in the size of granuloma (greater than 50 percent reduction) over a 6 week month period using the assigned treatment method.

Definition of failure: We are defining a treatment as a failure if after 6 weeks of treatment there is less than 50% reduction in the size of tracheostomy granulomas.

D. Description, Risks and Justification of Procedures and Data Collection Tools:

These methods of treatment do not represent a deviation of the standard of care for tracheostomy granulomas and incur the standard amount of risk.

The risks for administering steroid application include thinning of skin, local infection, and systemic absorption. Silver nitrate can cause superficial burning on normal tissue that is exposed. Betadine can cause skin irritation.

E. Potential Scientific Problems:

Potential scientific problems include the following:

1. Inability to enroll the number of patients needed to obtain data pertaining the success or failure of the three methods of treatment
2. Potential for bias in early failure between the 3 treatment arms. For example, it is possible that one treatment would work quickly and another would work slowly. If we discontinue follow-up too early, we would bias towards the early treatment effect. To minimize this risk we will continue to follow patients clinically with the treatment provided unless there is worsening of the granuloma that would require a change in treatment. There is the potential that this study is under powered. There is no data on the treatment of tracheostomy site granulomas and therefore the mean and variance in the treatment effect may be different than that estimated in our power analysis below. This study is powered to detect a clinically important difference and will additionally provide data to determine the sample size needed for future studies. We feel this potential is reasonable given that this study is a pilot study.

F. Data Analysis Plan:

Success and failure rates for each treatment method and the length of time between initial administration of the treatment and the determination of treatment success or failure will be utilized to compare the three standard of care treatment methods to better define and improve the current standard of care treatment of tracheostomy granulomas.

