All variable will be analyzed for distribution and cleaned. For inconsistencies, we will refer back to the source data. Data will be checked for normalcy and non-parametric tests will be utilized for non-normal data. All analyses will utilize an alpha of 0.05 with two tails. The study will utilize an intent to treat analysis where subjects are analyzed according to the treatment they were assigned to regardless of treatments they receive.

Aim 1: Test for difference in treatment failure between the three treatment arms

Hypothesis 1: At the primary time point (6 weeks), there will be a clinically important difference between the silver nitrate treatment and the topical treatments.

Aim 2: Test for difference in categorical granuloma improvement in the three treatment arms

Hypothesis 2: At the primary time point (6 weeks), there will be more categorical improvement in the silver nitrate treatment group compared to and the topical treatments.

Aim 3: Describe the treatment effects of the three treatment arms including average number of treatments needed (silver nitrate), duration of topical medication administration (Betadine and Hydrocortisone, i.e. two weeks versus three weeks)

Hypothesis 3: Descriptive aim, no specific hypothesis in this pilot study.

Power Analysis:

Power analysis is based on aim 2. Because tracheotomy site granulomas have not been rigorously studied in the literature, the degree of improvement that will be found in the treatment groups is unclear. We hypothesize that the standard deviation for this 5 point scale will be one unit of measure. We determined the power to detect a difference of one unit of measure between treatment groups (from partial response to resolution or from minimal improvement to improvement). Assuming a sample size of 15 and an alpha of 0.05, our study will have an 80% power to detect a 1.1 point difference in categorical granuloma improvement. Table 1 below shows the power to detect differences between two treatment groups.

Table 1: Power analysis for Aim 2

Treatment A mean	Treatment B mean	% Diff	Power
3.4	2.4	42%	78%
3.4	2.2	55%	91%
3.4	2.1	62%	94%
3.5	2.5	40%	78%
3.6	2.5	44%	85%
3.7	2.5	48%	90%

The power to detect differences in treatment success (Aim 1) is shown in table 2. This study has an 80 percent power to detect a clinically important (50 percentage point) difference in treatment success between two treatment arms.

Treatment A Success (%)	Treatment B Success (%)	Relative Risk*	Power

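### The exit rules in IV.C items 4 to 6 can end outcome collection before week 6, and no rule gives those patients a week-6 status in the intent-to-treat analysis

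*Combined protocol and SAP*

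**What the plan says.** **Time point and analysis set.** IV.C item 3: "Our primary time point will be 6 week follow up". Hypotheses 1 and 2 in IV.F use the same time point. IV.F defines intent to treat so that "subjects are analyzed according to the treatment they were assigned to regardless of treatments they receive".

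**Exits in IV.C.**
- Item 4: "If the investigator determines further follow-up is not necessary, per standard of care, the observation period will end". No worsening, resolution or response threshold is attached.
- Item 5: follow-up and participation end when the physician judges the granuloma to be worsening, whether or not another treatment is needed.
- Item 6: both end "if a patient is given a different form of treatment, such as in the emergency department or through a primary care physician", whether or not the granuloma has worsened.

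**Safeguard in IV.E item 2.** The protocol names the bias: "If we discontinue follow-up too early, we would bias towards the early treatment effect". Its answer is that "we will continue to follow patients clinically with the treatment provided unless there is worsening of the granuloma that would require a change in treatment".

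**Outcome definitions.** Success in IV.A.1a is a reduction above 50% "over a six week observation period using the assigned treatment". Failure in IV.A.1b is a reduction below 50% at the end of the six weeks, or worsening that calls for another treatment. The failure definition restated at the end of IV.C leaves out the worsening clause. IV.A.2 has size recorded at every time point and gives worsening a score of 0.

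**The concern.** The analysis needs a week-6 status for everyone assigned, but the exit rules stop collecting it in some patients. Nothing in the text says whether such a patient is scored on the last visit, dropped, or counted as a failure. IV.F also refers to "the length of time between initial administration of the treatment and the determination of treatment success or failure", which could be read as allowing an earlier determination, but no rule says that it replaces week-6 status.

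The exits could plausibly differ by arm. Topical treatment runs for two weeks with one possible extra week, while silver nitrate may be repeated at the first and second follow-up visits. A patient released early cannot show later regrowth or later response. At 15 per arm, a scoring choice made after the data are seen could decide a comparison. The estimates are also meant to inform the sample size of future studies.

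**Working it through.** **1. Which exits have a week-6 status?**

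| Exit | Condition in IV.C | Aim 1 status |
|---|---|---|
| Item 4 | Follow-up judged unnecessary | None stated |
| Item 5, other treatment needed | Worsening | Failure (IV.A.1b) |
| Item 5, other treatment not needed | Worsening | None stated |
| Item 6, with worsening that needed it | Different treatment | Failure (IV.A.1b) |
| Item 6, without worsening | Different treatment | None stated |

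In the last row, a patient with more than 50% reduction does not meet the success definition, which requires the assigned treatment, and does not meet the failure definition either. Separately, a reduction of exactly 50% fits neither definition, because success is above 50% and failure is below it.

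**2. Do the exits match the IV.E safeguard?** IV.E allows one exception: worsening that would require a change in treatment. Item 5 is wider (any worsening). Items 4 and 6 do not require worsening.

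**3. The plan's own power figures.** Inputs from IV.B and IV.F: 45 patients in three arms, so 15 per arm; SD 1; two-sided alpha 0.05. Normal approximation: power = Φ(d·√(n/2) − 1.96). For d = 1.1 and n = 15: 1.1 × √7.5 − 1.96 = 1.05, so power is 85.4% (Table 1: 85%). Differences of 1.0, 1.2 and 1.3 give 78.2, 90.8 and 94.5% (Table 1: 78, 90 to 91, 94). The stated power therefore assumes that all 15 per arm contribute an outcome.

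**4. Weight of one patient.** 1/15 = 6.7 percentage points of an arm's success rate. One category on the Aim 2 scale for one patient is 1/15 = 0.07 of the arm mean.

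**5. Scoring sensitivity.** Example from Table 2, 27% versus 73%, i.e. 4/15 versus 11/15. Lower-arm patients without a defined status are scored success instead of failure. The counts are assumed. The plan names no test, so two are shown.

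| Rescored | Lower arm | Difference (points) | Fisher p | Uncorrected chi-square p |
|---|---|---|---|---|
| 0 | 4/15 | 46.7 | 0.027 | 0.011 |
| 1 | 5/15 | 40.0 | 0.066 | 0.028 |
| 2 | 6/15 | 33.3 | 0.139 | 0.065 |
| 3 | 7/15 | 26.7 | 0.264 | 0.136 |

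Starting from the 20% row (3/15), it takes one more rescored patient to reach the same p-values. Equal rescoring in both arms would largely offset.

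**6. Upper bounds.** With k unscored patients in each arm, the best-to-worst range of the between-arm difference is 2k/15 wide: 13, 27, 40 and 53 points for k = 1 to 4. This ignores sizes recorded at earlier visits.

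**7. If unscored patients were dropped.** Aim 2 power at 1.1 points falls from 85% (n = 15) to 77% (n = 12) and 69% (n = 10). By t-test the figures are 83, 73 and 64%.

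**The case against.** - **Item 4 may concern only resolved granulomas.** It refers to follow-up not needed under standard of care, and the IV.E discussion is about a slow treatment being cut off, which release after resolution would not do. Item 4 also ends the observation period without saying, as items 5 and 6 do, that participation is complete. This stands in part. A reader might infer a flat contradiction between item 4 and IV.E, and the text does not support one that strong. But no resolution condition is written, and resolution at week 2 or 4 is not week-6 status.
- **Earlier sizes exist.** True, and they narrow the ranges in step 6 of the working. No rule carries them forward, though. Doing so could overstate success where there is regrowth to below 50% reduction, and understate it in a slow-acting arm, which is the bias IV.E describes.
- **Any trial of 15 per arm is sensitive to single patients, and IV.E concedes that power may be low.** This stands. The sensitivity is not special to this plan; the undefined scoring is.
- **Intent to treat fixes the arm, not the score.** Correct. Counting other treatment as failure fits IV.F as well as using the observed size does, so the plan has to choose.
- **The wording differences are minor.** Item 5 bases intent to treat on the treatment received, and IV.F on the treatment assigned. The former may be a slip, and the shorter failure definition may be abbreviated flow-chart text. Both still need aligning.

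**Conclusion.** The point holds as a gap in outcome collection and scoring. Items 4 to 6 can stop collection before the primary time point. No week-6 status is defined for item 4 exits, for item 6 exits without worsening, or for item 5 exits that need no other treatment. It should be fixed before analysis.

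Three stronger readings are not supported:
- **That one patient overturns the result.** In the 4/15 versus 11/15 example this is so only with Fisher's test; by chi-square it takes two. From 3/15 versus 11/15 it takes two by Fisher and three by chi-square.
- **That the comparison is biased in a known direction or by a known amount.** The documents give no exit rate and no direction by arm, and every count above is an assumption.
- **That power falls to 77% or lower.** This applies only if patients are dropped, which the IV.F analysis by assigned arm does not call for.

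Worsening that needs another treatment adds no gap for Aim 1 if IV.A.1b is applied. A figure near items 5 and 6 is not shown in the text reviewed, so any exit handling in it could not be checked.

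**What to change.** 1. In IV.C items 4 to 6, separate the end of clinical follow-up or assigned treatment from the end of outcome collection, and obtain the week-6 size measurement for every assigned patient. Treatment decisions are unaffected.
2. In IV.F, analyse all patients by assigned arm. State in advance one scoring rule for other treatment without worsening (failure, or observed week-6 size) and use the alternative as a sensitivity analysis. If observed size is chosen, amend the assigned-treatment condition in both success definitions (IV.A.1a and the restatement at the end of IV.C).
3. State whether Aim 2 uses score 0 or the week-6 category after a worsening exit. Add a best-case/worst-case analysis for week-6 values still missing.
4. Assign a reduction of exactly 50% to one category. State that the IV.F time to determination is a separate measure and does not replace week-6 status.
5. Reconcile items 4 to 6 with IV.E, the restated failure definition with IV.A.1b, and treatment received in item 5 with treatment assigned in IV.F.

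**Cost:** wording, one or two sensitivity analyses, and at most one week-6 visit per early-exit patient, within the planned six-week schedule. Some of these may become research visits rather than standard-of-care visits, because items 5 and 6 now treat participation as complete.

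### Section IV.C item 5 places patients given other treatments by treatment received, Section IV.F by treatment assigned, and nothing says which text governs

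*Combined protocol and SAP*

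**What the plan says.** Four parts of the combined protocol and SAP bear on the analysis arm.

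- **Section IV.C item 5** ends participation when the granuloma is worsening. For the case where other treatments are used, it then says "we will analyze with the intent to treat analysis based on the treatment the subject was received".
- **Section IV.F (Data Analysis Plan)** defines intent to treat for the whole study: "subjects are analyzed according to the treatment they were assigned to regardless of treatments they receive".
- **The success definitions** tie the outcome to the assigned treatment, in Section IV.A 1.a ("over a six week observation period using the assigned treatment") and again after the flow chart in IV.C ("over a 6 week month period using the assigned treatment method").
- **The handling of a change of treatment.** Section IV.A 1.b counts a patient as a failure "or if worsening occurs requiring alternative treatments", and IV.A 2.b gives worsening a score of 0. Section IV.C item 6 also ends participation "if a patient is given a different form of treatment, such as in the emergency department or through a primary care physician".

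**The concern.** Item 5 and IV.F use the same label and cover the same patients, those who get something other than what they were allocated. Read literally, one places such a patient by treatment received and the other by assignment. Item 5 is the more specific provision, so a reader who lets the specific rule override the general one would follow it.

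That reading has a particular defect here. Items 5 and 6 end participation at worsening or at a change of treatment, so no study outcome is observed on the second treatment. Moving the patient would therefore charge the second arm with a result that arose before its treatment was given. With about 15 patients per arm, the placement of a single patient can be visible in both Aim 1 and Aim 2.

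**Working it through.** **The texts side by side**

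| Place | Patients covered | Arm used |
|---|---|---|
| IV.C item 5 | those given other treatments | treatment received (garbled) |
| IV.F | all | treatment assigned, whatever was received |
| IV.A 1.a; IV.C after flow chart | all (success definition) | assigned treatment |

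The first two rows give different arms for a patient who switches between study treatments. No sentence ranks them.

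**The plan's own figures.** Total N is 45 over three arms, so 15 per arm; alpha is 0.05 two-sided; SD is 1 for Aim 2.

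- Table 1, row 3.6 vs 2.5, normal approximation: power = Φ(1.1/√(2/15) − 1.96) = 0.854, against 85% stated. The other five rows also reproduce.
- Table 2, pooled-variance normal approximation, k/15 vs 11/15 for k = 9 down to 3: 0.116, 0.200, 0.313, 0.450, 0.602, 0.750, 0.874, against 12, 20, 30, 44, 60, 74 and 87% stated.

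Neither table depends on how switchers are placed, so no planned figure changes under either reading.

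**Illustration for Aim 1.** Assumptions, none from the documents: exactly one switcher, who is a failure under IV.A 1.b; a two-arm comparison; Fisher's exact test, since the protocol names no test for Aim 1. Moving one failure changes only the denominators: a/15 vs 11/15 becomes a/14 vs 11/16 (poorer to better arm) or a/16 vs 11/14 (better to poorer arm).

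| Table 2 row | a | p, as assigned | p, poorer to better | p, better to poorer |
|---|---|---|---|---|
| 20% | 3 | 0.009 | 0.014 | 0.003 |
| 27% | 4 | 0.027 | 0.066 | 0.009 |
| 33% | 5 | 0.066 | 0.141 | 0.014 |
| 40% | 6 | 0.139 | 0.269 | 0.033 |
| 47% | 7 | 0.264 | 0.457 | 0.072 |
| 53% | 8 | 0.450 | 0.707 | 0.142 |
| 60% | 9 | 0.700 | 1.000 | 0.260 |

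The result crosses 0.05 in 3 of the 14 moves: the 27% row (poorer to better) and the 33% and 40% rows (better to poorer). In the other 11 it does not.

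For the 27% row the gaps are:

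- as assigned: 11/15 − 4/15 = 46.7 points
- poorer to better: 11/16 − 4/14 = 68.8 − 28.6 = 40.2 points
- better to poorer: 11/14 − 4/16 = 78.6 − 25.0 = 53.6 points

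If the second treatment is not a study treatment, the patient simply leaves the comparison:

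- from the poorer arm: 11/15 − 4/14 = 44.8 points, p = 0.027
- from the better arm: 11/14 − 4/15 = 51.9 points, p = 0.009

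**Illustration for Aim 2.** Row 3.6 vs 2.5, one patient with the worsening score of 0, assumed to be carried to week 6 (the plan does not say so). Moving a 0 leaves each arm's total unchanged.

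- Poorer to better: 15×3.6/16 − 15×2.5/14 = 3.375 − 2.679 = 0.70
- Better to poorer: 15×3.6/14 − 15×2.5/16 = 3.857 − 2.344 = 1.51
- Leaves from the poorer arm: 3.6 − 2.679 = 0.92
- Leaves from the better arm: 3.857 − 2.5 = 1.36

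The difference by assignment is 1.1 throughout.

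**The case against.** The strongest reply is that the plan already answers the question. IV.F is the analysis section, it defines intent to treat, and its definition expressly covers patients who receive something else. Item 5 is a follow-up rule that borrows the term. Because participation ends when treatment changes, the treatment received while in the study is ordinarily the assigned one; if the broken verb was meant as *was receiving* or *had received*, item 5 leads to the same arm as IV.F. This makes assignment the likely intent. It does not make the clause correct as written: more than one repair fits the broken grammar, and the literal one contradicts IV.F.

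The second reply is that the numbers are driven by assumptions, and this also stands in part. The choice of test matters. With a pooled-variance z test, the kind of calculation that reproduces Table 2, the 27% row goes from p = 0.011 to 0.028 when a failure moves from poorer to better, and does not cross 0.05. Crossings fall to 2 of 14, in partly different cells (33% row poorer to better, 0.028 to 0.070; 40% row better to poorer, 0.065 to 0.024). Aim 1 also concerns three arms, whereas the illustration compares two, and the Aim 2 example uses the lowest score on the scale. The figures show only that one patient can matter; the inconsistency does not rest on them.

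**Conclusion.** The concern holds, as a minor point. The current text states the analysis arm in two ways for patients given another treatment and does not rank them. Assignment is the probable intent, and an analyst who follows IV.F introduces no bias.

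If item 5 were followed literally, failures could be counted against an arm whose treatment had not been given when they arose. The direction and size of the resulting bias cannot be stated, because the documents give neither the number of switchers nor which way they would go. Under the assumptions shown, one moved failure shifts the 27% vs 73% comparison from 46.7 points to 40.2 or 53.6, and the 1.1-point Aim 2 difference to 0.70 or 1.51. Whether significance changes depends on the row, the direction and the test. With no switchers, nothing changes.

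**What to change.** Reword the last clause of Section IV.C item 5 so that patients who are given other treatments are analysed according to the treatment assigned, in line with IV.F and both success definitions. If an as-received analysis is also wanted, name it separately as a sensitivity analysis rather than as intent to treat. Make the change before outcomes are compared by arm.

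The cost is one reworded clause. It needs no added visits, patients or data collection, leaves sample size and power as they are, and does not touch clinical management.

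### The time to determination of success or failure in IV.F pools a good and a bad outcome, so on no reading of the protocol does it measure how fast a treatment works

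*Combined protocol and SAP*

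**What the plan says.** The opening sentence of IV.F (Data Analysis Plan) names two measures for comparing the arms. One is the success and failure rates. The other is a duration: "the length of time between initial administration of the treatment and the determination of treatment success or failure will be utilized to compare" the three treatments. The rest of IV.F gives this duration no aim, hypothesis, event definition, censoring rule or named test, although it sets a two-sided alpha of 0.05 for all analyses.

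When an outcome counts as determined depends on other sections:

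- **IV.A item 1a, success:** "clinically significant decrease in the size of granuloma (greater than 50% improvement) over a six week observation period".
- **IV.A item 1b, failure:** less than 50% reduction "at the conclusion of the six week observation period or if worsening occurs requiring alternative treatments".
- **IV.C, definitions under the flow chart:** success is again tied to 6 weeks. For failure: "We are defining a treatment as a failure if after 6 weeks of treatment there is less than 50% reduction". There is no worsening route here.
- **IV.C item 5:** if the physician finds that the "granuloma is worsening, the follow-up period will end", and participation is complete.
- **IV.C item 4:** "If the investigator determines further follow-up is not necessary, per standard of care, the observation period will end". The protocol does not say how such a patient is classified or timed.
- **IV.C item 6:** a different treatment given elsewhere also ends participation.
- **IV.E item 2:** "it is possible that one treatment would work quickly and another would work slowly". The same item says patients stay in follow-up unless the granuloma worsens enough to need a change of treatment.

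Visits are two-weekly, within 3 days either side, and IV.A item 2a has granuloma size recorded at each time point.

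**The concern.** A duration used to compare treatments needs one kind of event at its end, so that shorter or longer has a meaning. This one ends at success or at failure. It could therefore be short because a treatment worked early or because it failed early, and the protocol's definitions do not settle which. IV.E recognises that the arms may differ in speed, and this is the only time-to-outcome comparison in the plan. If it were analysed as written, a difference between arms could come entirely from when failures were noticed, and a real difference in speed of response could leave no trace in it.

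**Working it through.** The documents give no power, event count or expected value for this duration, so there is no stated figure to reproduce. The check is to apply each set of rules and see what the duration records.

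**Inputs.** From the documents: 15 patients per arm (IV.F, Power Analysis); visits at about weeks 2, 4 and 6 (IV.C item 4); 73% success, which is 11/15, as in the Treatment B column of the Aim 1 power table. Assumed for illustration: the week at which each patient's outcome is determined.

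**Formula.** Mean time = sum of (patients × week of determination) / 15.

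**Reading 1: IV.A definitions.** Successes and failures without worsening are determined at week 6; only worsening is determined earlier.

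- Arm A, 11 successes and 4 failures found at week 6: (15×6)/15 = 6.0 weeks.
- Arm B, 11 successes and 4 failures by worsening at week 2: (4×2 + 11×6)/15 = 74/15 = 4.93 weeks.
- Difference: 6.0 − 4.93 = 1.07 weeks, with identical success rates. The shorter time belongs to the arm whose failures came sooner.
- An arm with all 11 responders past the 50% mark by week 2, and an arm with all 11 past it only at week 6, neither with worsening: 6.0 weeks in both. A 4-week difference in response does not register.

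**Reading 2: flow-chart definitions.** Success and failure are both fixed at 6 weeks. Every patient who completes follow-up scores about 42 days, between 42 − 3 = 39 and 42 + 3 = 45 with the visit window. What variation remains reflects appointment dates. Patients stopped early for worsening have no defined time.

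**Reading 3: IV.A definitions, with observation also ending early on response under IV.C item 4.**

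- Good arm, 11 successes at week 2 and 4 failures at week 6: (11×2 + 4×6)/15 = 46/15 = 3.07 weeks.
- Poor arm, 11 worsenings at week 2 and 4 successes at week 6: (11×2 + 4×6)/15 = 3.07 weeks.
- Opposite results give the same value.

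**The same patients scored as time to response, with worsening as a competing event.**

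- Early against late responders under reading 1: response by week 2 is 11/15 = 73% against 0%; by week 6 it is 73% in both. The difference in speed shows.
- Reading 3: the good arm has 73% response and no worsening by week 2. The poor arm has no response and 73% worsening by week 2, then 4/15 = 27% response by week 6. The two arms separate.

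**The case against.** The strongest reply is that the text does not support a claim of consistent reversal. A reader might infer that only failure can be determined early, so that a shorter time always marks the worse arm. That holds only under the IV.A definitions. IV.C item 4 lets the investigator end observation early for reasons other than worsening, which plausibly covers a resolved granuloma. Item 6 ends participation when another provider changes the treatment. The failure definition under the flow chart has no early route at all. This part of the reply stands: across the whole protocol the direction is ambiguous.

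A reader might also infer that the trial cannot show speed of response. It can. Size is recorded at each visit, and Aim 3 reports the number of silver nitrate treatments and two versus three weeks of topical treatment. Because repeat or extended treatment depends on residual granuloma, those counts carry some information on speed. The weakness is confined to this variable.

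Finally, IV.F never says that a shorter time is better, it sets the duration beside the success and failure rates, and it might be read as intending separate times to success and to failure. That limits the harm, but it does not rescue the measure as written: one duration covering both outcomes is named as a basis for comparison, and nothing in IV.F separates them. Nor do the other routes to an early end make it a measure of speed; they only change how it falls short.

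**Conclusion.** The point holds in this form: the duration in IV.F pools opposite outcomes. It tracks early failure under the IV.A definitions, is nearly constant under the flow-chart definitions, and has no direction if observation can end early on response. On none of these does it measure speed of response.

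The sizes shown (1.07 weeks apart with equal success; 3.07 weeks in two opposite arms; a 4-week difference hidden) rest on assumed outcome patterns with 15 per arm. They show what can happen and are not forecasts. The documents do not support saying that the analysis would systematically favour the worse arm.

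The consequence is moderate. The week-6 comparisons in Aims 1 and 2 and both power tables do not depend on this variable. It should still be corrected, because it is a stated between-arm comparison that can mislead and the data for a sound replacement are already being collected.

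**What to change.** Replace the duration in IV.F with time to response, and state the following:

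- **Event:** the first scheduled visit (week 2, 4 or 6) at which recorded size is more than 50% below baseline.
- **Competing event:** worsening, or a change of treatment, before response.
- **Early end under IV.C item 4:** use the last recorded size. If it is more than 50% below baseline, the patient is a responder at that visit; otherwise the patient is censored at that visit for the time analysis.
- **No event by week 6:** counted as not having responded.
- **Report:** for each arm, the cumulative proportion with response and, separately, the cumulative proportion with worsening or change of treatment, by weeks 2, 4 and 6.
- **Status:** secondary and descriptive. The week-6 success/failure comparison stays as it is for Aim 1.

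The sponsor should also reconcile two pairs of passages, since both affect how patients are classified: IV.C item 4 (observation may end when further follow-up is judged unnecessary) with IV.E item 2 (follow-up continues unless there is worsening), and the failure definition in IV.A item 1b with the one under the flow chart in IV.C.

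The cost is a short paragraph in IV.F plus the two reconciliations. No new data, visits or patients are needed. The limitations are that response time is known only to the two-week visit grid, and that 15 patients per arm will give imprecise proportions.
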